Preliminary Data

Preliminary work has provided partial support of H1 regarding feasibility of the study. We are conducting a partial test of our experiment (without alcohol administration) with a community sample examining the effects of the mood induction on mood and suicide-related attentional bias (Launched 10/11/19; currently paused due to COVID19 safety concerns). Using similar recruitment procedures, 86 individuals have been screened; 55 met inclusion criteria; 41 attended a study session; 35 remained eligible after in-person screening; 1 withdrew before completing the procedures. Thus, we had preliminary data from 34 participants. There was group equivalence in mood prior to mood induction (ps = .39-.81). *T*-tests revealed effectiveness of the mood induction. The negative mood group reported higher post-manipulation sadness (p=.001, Cohen's d=1.24) and guilt (p=.001, d = 1.21) and guilt (p=.001, d = 1.21)

and lower joviality (p=.05, d = .68) compared to the positive mood group. These were medium to large effects despite 5 participants claiming the mood induction was ineffective in post-study interviews.

Preliminary analyses showed that the distribution and variability in the suicide-related attentional bias scores (M=10.17, SD=41.32) were similar to that of prior studies²⁸ of nonsuicidal subjects (M=3.96, SD=58.48, d=0.12). Preliminary analyses supported the anticipated direction of effect of mood on suicide-related attentional bias. The sample size for this analysis was reduced to 23 due to missing data on Stroop (software malfunction, n=2), mood induction and study aims deception failure (n=6), and exclusion of error trials (reducing analysis sample by 5). Although not statistically significant, the negative mood group showed more suicide-related attentional bias (M=15.77, SD=31.33) than the positive mood group (M=2.45, SD=48.24, d=.32). The negative mood group also had more depressive-related attentional bias (M=4.83, SD=58.48) than the positive mood group (M=-6.70, SD=41.96, d=.23). These data provide empirical support for the proposed study aiming to further test the feasibility of our procedures and hypotheses guided by the AAM.

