COVER PAGE

Official Study Title: Acute Use of Alcohol and Attentional Bias Towards Suicide: An Experimental Test of the Attention-Allocation Model

NCT number: NCT04276779

Date of the document: December 1, 2023

Statistical Design and Power

Statistical Design

Data from Qualtrics (Session 1 baseline data), excel (paper data entered from Session 1 and 2), and DirectRT software will be exported into IBM SPSS statistical software, Version 25. Standard data quality checks and cleaning procedures will be completed. Most notably, any participants voicing awareness of the study aims or not responding adequately to the mood induction will be removed from the initial analyses. Second, manipulation checks will be performed by comparing the participants in the mood conditions on self-reported mood post-manipulation. We expect that negative mood participants will have greater mean scores on the guilt and sadness subscales and lower mean scores on the joviality subscale compared to the positive mood participants.

Study variables for the entire sample will be examined using descriptive statistics such as frequencies and percentages (for categorical variables) and means, standard deviations, and ranges (for continuous variables) to ensure values are reasonable. Prior to conducting analyses related to the hypotheses of the study, individual distributions of continuous variables will be examined visually with histograms to confirm that all assumptions for the analyses are reasonably met. Methods robust to distributional assumptions will be used as appropriate.

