Prior to analysis, Suicide Stroop scores will be evaluated for outliers. We will exclude: trials with incorrect responses, trials with response latencies ± 2 SD from each participant's mean response latency, participants with a mean response latency ± 2 SD from the overall sample's mean, participants whose error rate was +2 SD above the error rate for all participants. We will also examine the reliability, factor structure, and concurrent validity for the suicide-related alcohol expectancies measure (created for this study) prior to its use for Hypothesis 3. We will use exploratory factor analysis (with parallel analysis), Cronbach's alpha, and examine associations with AUDIT total scores and past suicidal ideation severity. Finally, we will confirm there were no pre-existing relevant differences in mood states between our mood and alcohol conditions by estimating measures of association (i.e., R²) between condition assignment and pre-manipulation sad, guilty, and joviality mood states.

Pre-Pilot tests: To finalize study procedures, for the 10 pre-pilot subjects, we will examine prevalence of mood induction effectiveness. If >50% fail the mood induction, we will replace it with another effective mood induction (imaginative film). We will also run frequencies to examine percentage of participants who are successfully deceived, expecting these percentages to be high (>90%). We will use these results to adjust the protocol in order to improve success of our mood manipulation and deception.

Specific Aim 1, Hypothesis 1a: To test the feasibility our experiment, we will first quantify the number of individuals who contact our lab about the study and the percentage who are eligible and participate. We will run descriptive statistics to quantify 1) prevalence of successful mood induction (expecting at least 75%), 2) distress ratings after the study session (expecting average ratings to be low), and 3) number of adverse events (expecting less than 1% of pilot subjects). **Objective 1b:** Using measures of effect size (i.e., Cohen's d, Cramer's V) and t-tests and Chi square analyses, we will examine sociodemographic differences (gender, age, race/ethnicity, income, and alcohol use history) in these feasibility factors.

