Specific Aim 2, Hypothesis 2: Examine sociodemographic differences in suicide-related attentional bias. Suicide-related attentional bias will be higher among women, individuals with lower income, individuals ages 21-34, and individuals with heavier alcohol use than their comparators. Although racial differences are not observed in suicide attempts, we will explore racial differences in suicide-related attentional bias.

Analysis: Using measures of effect size and *t*-tests and Chi Square analyses where appropriate, we will examine potential these sociodemographic differences in suicide-related attentional bias scores.

Specific Aim 3, Hypothesis 3: Examine the conditional effect of AUA on suicide-related attentional bias by mood states. Individuals in the alcoholic beverage-negative mood condition will exhibit the greatest suicide-related attentional bias, followed by individuals in the placebo beverage-negative mood condition, placebo beverage-positive mood condition, and alcoholic beverage-positive mood condition.

Analysis: The interactive effect of mood and alcohol (Alcohol X Mood Induction) on attentional bias towards suicide-related cues (Stroop interference score, calculated by subtracting the response latencies for neutral words from the latencies for suicide-related words) will be estimated using a general linear model of the form $\hat{Y} = \beta_0 + \beta_1 Alcohol + \beta_2 Mood + \beta_3 Alcohol \times Mood$, where \hat{Y} is the average Stroop interference score, *Alcohol* is a binary indicator (1=yes, 0=no) of assignment to alcoholic beverage intake, and *Mood* is a binary indicator of assignment to the positive vs. negative mood induction (1 vs. 0). Among the positive mood induction group, the average effect of alcohol intake on Stroop interference scores is estimated by the sum of coefficients $\beta_1 + \beta_3$, while the average effect of alcohol intake in the negative mood induction group is estimated by the coefficient β_1 . Therefore, the coefficient β_3 estimates the differential effect of alcohol intake conditional on mood induction. We will use model-predicted means to estimate mean Stroop interference scores among the negative mood-alcohol condition participants. Measures of effect size (e.g. R², partial eta², Cohen's d) will be used to aid in interpretation. Inferences will be conducted using confidence intervals for the comparisons of interest, as statistical significance testing is not the primary goal of the study.

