For this training grant, as a compromise between feasibility and precision of estimates, I propose to recruit 10 pre-pilot subjects and 150 subjects (approximately 38 per condition combination) over a 2.5-year period. Assuming that 25% of subjects may be excluded due to mood induction failure, we will have 30 subjects per condition. Rather than traditional significance testing, the goal of the project is to examine feasibility and tolerability of procedures and explore observed effect sizes. Inference will be conducted primarily by estimation of 68% confidence intervals to be used as reasonable ranges for observed effect sizes. Following the proposed analysis of Hypothesis 3, it can be shown using variance algebra that the standard error of the effect of alcohol intake on Stroop interference scores within each of the mood induction groups (positive or negative) is $SE_{Alco.Eff} = \sigma \sqrt{2/n}$, where σ is the standard deviation of the Stroop interference scores and *n* is the sample size per condition combination. Thus, the standard error of the differential effect of alcohol intake conditional on mood induction (i.e. the interaction term) is $SE_{Diff.Alco.Eff} = 2\sigma/\sqrt{n}$. With n = 30 and standardizing the Stroop interference scores (i.e. $\sigma = 1$) to express the confidence interval in terms of an effect size (Cohen's d), the half width of a 68% confidence interval for the standardized effect of alcohol intake within each of the mood induction groups is .26 and the half width of a 68% confidence interval for the standardized differential effect of alcohol intake conditional on mood induction is .36, which provide reasonable and tolerable uncertainty ranges.

For completeness, in terms of null hypothesis significance testing (not a primary goal of this study), at a significance level of .05 the sample size provides 80% power to detect a standardized effect of alcohol intake

within each of the mood induction groups of .72, and standardized differential effect of alcohol intake conditional on mood induction of 1.

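### The SAP excludes mood-induction failures after randomisation by an undefined criterion and plans no all-randomised H3 or H4 model, so the negative-v-positive mood contrast is open to selection bias

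*SAP*

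**What the plan says.** The SAP's Statistical Design section states, as part of data cleaning, that "any participants voicing awareness of the study aims or not responding adequately to the mood induction will be removed from the initial analyses". Neither document says which instrument or threshold decides whether a response was adequate, or what counts as voicing awareness. The next sentence reads "Second, manipulation checks will be performed by comparing the participants in the mood conditions on self-reported mood post-manipulation", and it names no analysis set. The full sample is mentioned once, for description: "Study variables for the entire sample will be examined using descriptive statistics".

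The SAP's Power and Sample Size section builds the exclusion into H3: "Assuming that 25% of subjects may be excluded due to mood induction failure, we will have 30 subjects per condition". Under Specific Aim 3, Mood is coded by assigned induction, but again no analysis set is given. The hypothesis there is an ordering of all four cells, with alcohol-negative highest, "followed by individuals in the placebo beverage-negative mood condition, placebo beverage-positive mood condition, and alcoholic beverage-positive mood condition". Two negative-above-positive comparisons are therefore part of the prediction. Specific Aim 4 (H4) names no analysis set either. The wording about initial analyses hints at later ones, but neither document describes any.

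On timing, the protocol gives the beverage first, then the mood induction, then the PANAS-X and the Stroop. Deception failures are assessed in the safety interview after the Stroop.

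**The concern.** Whether someone responds to the mood induction is known only after both manipulations and may depend on both. Removing non-responders drops people whose mood did not worsen in the negative arm and people whose mood did not improve in the positive arm. The selection therefore runs in opposite mood directions in the two arms, and the groups left are no longer those that randomisation formed.

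The pilot's stated purpose is to explore effect sizes, so their size is the product. Part of a negative-above-positive Stroop difference could come from the exclusion rule. A manipulation check run on the retained people would overstate the strength of the induction. A shift in the alcohol-by-mood interaction would go unseen, because neither removals by cell nor an all-randomised estimate is planned. Hypothesis 1a reports the prevalence of successful induction, which discloses the failure rate but corrects none of these estimates.

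**Working it through.** **The plan's own figures.** With SD 1 and n=30 per cell, the standard errors are √(2/30)=.258 for alcohol within a mood group and 2/√30=.365 for the interaction. The 68% half-widths are .994×.258=.26 and .994×.365=.36, as stated. Effects detectable with 80% power at two-sided .05 are 2.80×.258=.72 and 2.80×.365=1.02, against the stated .72 and 1. These reproduce. A 25% loss from 150 leaves 112.5, or 28.1 per cell rather than 30; that is a separate matter, but it affects the power comparison under the fix.

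**Inputs.**
- Failure rates: 25% (SAP, Power and Sample Size) and 15% (5 of 34 in the protocol's Preliminary Data, if all 34 were asked).
- Correlations and splits by beverage arm: assumptions, shown as ranges.

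**Effect of removal.** If the least responsive fraction f is removed from a normal distribution, the mean responsiveness of those kept is m = φ(z_f)/(1−f). This gives m=.274, .350, .424, .497 and .570 at f=.15, .20, .25, .30 and .35. The kept variance is .641 at f=.15 and .535 at f=.25.

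**H3 mood contrast, no true effect, equal failure rates.** Let r be the correlation with the Stroop score.
- If the score rises with negative mood, the negative arm shifts by +mr and the positive arm by −mr, so the bias is 2mr. At 15% failures this is 2×.274×(.1 to .3) = .05-.16 SD. At 25% it is 2×.424×(.1 to .3) = .08-.25 SD.
- If the score tracks general responsiveness, both arms shift by +mr and the bias is zero.
- If the sign is reversed, the bias is −2mr.
- If only the negative arm loses 25%, the first case gives .424×(.1 to .3) = .04-.13 SD.

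For scale, the protocol's preliminary mood contrast is d=.32, itself from a sample already reduced by such exclusions. The Stroop split-half of .49 means that r=.3 needs an underlying correlation of .3/√.49=.43, so .3 is towards the high end.

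In the first case, with 30 per cell and no true effect, a 68% CI for placebo-negative v placebo-positive lies wholly on the predicted side with probability 1−Φ(.994−bias/.258). That is 22-36% at 15% failures and 25-50% at 25%, instead of 16%.

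**Manipulation check, if run on the reduced set.** Let ρ be the correlation of the failure criterion with the checked score. If both arms lose the same fraction, d becomes (d₀+2mρ)/√(1−ρ²(1−kept variance)). Starting from the protocol's d=1.24 for sadness:
- ρ=.3: 1.43 at 15% and 1.53 at 25%.
- ρ=.5: 1.59 at 15% and 1.77 at 25%.
- Only the negative arm loses 25% (mρ replaces 2mρ, and the two arms' variances are averaged): 1.38 at ρ=.3 and 1.50 at ρ=.5.

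**Alcohol contrasts.** With equal failure rates and correlations in the two beverage arms, the bias in β1, β1+β3 and β3 is zero. Otherwise, in the signed-mood case:
- Unequal failure rates, the same in both mood groups: β3 shifts by 2r(m_high−m_low) in absolute size. For 20% v 30% this is 2×(.1 to .3)×(.497−.350) = .03-.09 SD. For 15% v 35% at r=.3 it is 2×.3×(.570−.274) = .18 SD.
- Equal failure rates but r=.1 in one beverage arm and .3 in the other: 2×.2×m = .11 SD at 15% and .17 SD at 25%.

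The stated half-width for β3 is .36. The sign depends on which beverage arm is affected more, which the documents do not let one predict.

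**The case against.** The exclusion is declared in advance and built into recruitment, H1a reports the induction success rate, and inference is by 68% intervals in a pilot. Analysing people in whom the induction worked is a defensible choice for a mechanistic question. All of that stands, and it is why the planned analysis should be kept rather than replaced.

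A reader might infer from the order of the sentences that the manipulation check is inflated. The documents do not establish this. No set is named, the word introducing the check may only number a list, and the one precedent points the other way. The partial test apparently kept the failures when it reported mood effects: "These were medium to large effects despite 5 participants claiming the mood induction was ineffective in post-study interviews". There, induction and deception failures are mentioned as removed only for the Stroop comparison.

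A reader might also infer that any correlation between mood response and the Stroop score biases the mood contrast towards the prediction. It does not. The direction needs the score to rise with negative mood. That is H3's own premise, but it remains an assumption here.

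Finally, the contrasts that the SAP defines by coefficient and sizes are the alcohol contrasts, which are unbiased when failure rates and correlations match across beverage arms. The mood contrast enters through the hypothesised ordering. This limits the point but does not remove it: alcohol precedes the induction and could alter response to it, and no planned output would show whether it had.

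**Conclusion.** The concern holds in a limited form. What rests on the text alone is that exclusion depends on a post-randomisation response with no stated criterion, that H3 is sized on what remains, and that no all-randomised H3 or H4 model or tabulation of removals by cell is specified. For H4, the exclusion is inferred from the general wording on initial analyses; the sample-size text mentions only H3.

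The sizes are conditional. At the upper end, the mood-contrast bias of .25 SD approaches the preliminary d of .32, but that takes 25% failures in both arms, r=.3 and a score that follows negative mood. For the check, the supportable defect is an unnamed analysis set. If the reduced set were used, the conclusion that the induction works would survive but its magnitude would not. Bias in the alcohol contrasts is possible, not shown. The awareness exclusion is also applied after randomisation, but the documents give no basis for a direction or size, and none is claimed.

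This is a cheap improvement to make before analysis, not a flaw that makes the design unworkable.

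**What to change.** Suggested SAP wording: *Manipulation checks will be run on all randomised participants before any exclusion. H3 and H4 will be estimated in all randomised participants with a usable Stroop score, in their assigned cells, and reported beside the analysis that excludes mood-induction failures and aware participants. Removals will be given for each of the four cells.* Before the data are analysed, also fix the instrument and cut-off for an inadequate mood response and the definition of awareness.

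The cost is SAP text and one extra set of estimates, with no new data. The downside is dilution. If failures have no mood effect, an interaction of 1 among responders becomes .75 at 25% failures. Power is then Φ(.75/.327−1.96)=63% at 37.5 per cell, against Φ(1/.377−1.96)=76% at the 28.1 per cell that 25% exclusion leaves, or Φ(1/.365−1.96)=78% at the stated 30. The larger set partly offsets this, with 68% half-widths of .23 and .32 instead of .26 and .36, before any loss of Stroop data. The responder analysis remains available, so nothing planned is lost.

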Session 2. Participants who remain eligible will be scheduled for a second appointment, which will be one to ten hours in duration, depending on their randomly-assigned condition (i.e., alcohol vs. placebo). When scheduling Session 2, participants will be told to refrain from drinking alcohol or using recreational drugs 24 hours prior to the session and to refrain from eating four hours prior to the session. Upon arrival at the laboratory, eligibility will be confirmed, including a breathalyzer test to ensure a zero BrAC and field sobriety test for comparison post-detoxification. Those with nonzero BrAC will be rescheduled. Female participants will be given a pregnancy test kit and asked to produce a urine sample in a private bathroom located adjacent to

the laboratory (those with positive tests will be excluded). Height and weight will be measured to calculate alcohol dosage. We will assess pre-manipulation mood via the Positive and Negative Affect Schedule-Expanded Form (PANAS-X)–sadness, guilt, and joviality subscales³⁸ and 2-item Brief Hopelessness Measure.³⁹

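### Pre-manipulation mood is used only in an R² check that cannot confirm balance; it would serve better as a covariate, clearly in the mood check and modestly in the Hypothesis 3 model

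*SAP*

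**What the plan says.** The Protocol (Procedures, Session 2) collects mood before the drinks and the mood induction: "We will assess pre-manipulation mood via the Positive and Negative Affect Schedule-Expanded Form", using the sadness, guilt and joviality subscales.

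The SAP gives these scores one analytic use. Under Statistical Design it states that "we will confirm there were no pre-existing relevant differences in mood states between our mood and alcohol conditions", and that this is done "by estimating measures of association (i.e., R²) between condition assignment and pre-manipulation sad, guilty, and joviality mood states". It sets no value of R² that would count as relevant and names no consequence if one is found.

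The scores do not appear in the two analyses where they could help:

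- **Mood check** (SAP, Statistical Design): "manipulation checks will be performed by comparing the participants in the mood conditions on self-reported mood post-manipulation". No pre-manipulation term is mentioned.
- **Hypothesis 3** (SAP, Specific Aim 3, Analysis): the interaction "will be estimated using a general linear model of the form" that contains alcohol, mood and their product, and nothing else.

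On size, the SAP's power section states: "Assuming that 25% of subjects may be excluded due to mood induction failure, we will have 30 subjects per condition".

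**The concern.** A small R² in a sample of this size is weak evidence of balance, and a moderate R² is weak evidence of imbalance. The check therefore cannot deliver the confirmation that the SAP asks of it. Because no action is attached, an analyst who sees a difference must decide after the fact whether to adjust. Naming the covariate in advance closes that choice.

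The data for a better use are already collected. A subscale's own earlier value is the natural covariate for its later value, and the mood check is the evidence that the induction worked. In the Hypothesis 3 model, a chance difference in baseline mood between cells feeds into the alcohol-by-mood estimate to the extent that mood predicts the Stroop interference score.

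**Working it through.** **Inputs from the documents.** 150 randomised in the pilot, 25% assumed excluded, 68% intervals and σ = 1 (SAP, Power and Sample Size Considerations). Split-half reliability of the interference score is .49 (Protocol, Manipulation Check and Dependent Variable Measurement).

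**Not in the documents.** The correlation of baseline mood with the interference score, and the pre-post correlation of the mood subscales. Ranges are assumed for both.

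**1. The SAP's own half-widths.** For a 68% interval z = 0.9945. At n = 30 per cell:
- alcohol effect within a mood group: 0.9945 × √(2/30) = .257 (SAP: .26)
- interaction: 0.9945 × 2/√30 = .363 (SAP: .36)

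Both reproduce.

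**2. Cell size.** 150 × 0.75 = 112.5, or 28.1 per cell. Thirty per cell after 25% loss would need 120/0.75 = 160 randomised. At 28 per cell the half-widths are .266 and .376.

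**3. What the R² check can show at 28 per cell (N = 112).**
- 95% chance range of a baseline difference: ±1.96 × √(2/28) = ±.52 SD between two cells; ±1.96 × √(2/56) = ±.37 SD between the two mood (or two beverage) conditions.
- Expected four-cell R² under perfect randomisation: 3/(112 − 1) = 2.7%. Its 95th percentile, from a Beta(1.5, 54) distribution, is 6.9%.
- A difference of d SD between two equal groups has R² = d²/(d² + 4). At d = 0.4 this is 0.16/4.16 = 3.8%, well inside the four-cell chance range.
- If R² is instead computed for each two-level factor, the expected value is 1/111 = 0.9% and the 95th percentile 3.4%. A true 0.4 SD difference would then be detected at the 5% level only 56% of the time.
- If the check uses all 150, the chance ranges are still ±.45 SD (two cells) and ±.32 SD (two conditions).

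**4. Mood check with the matching pre-score.** For 56 v 56 and one covariate, the SE ratio is √[(1 − r²)(1 + 1/108)].

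| Assumed pre-post r | SE ratio | Reduction |
|---|---|---|
| .3 | .958 | 4% |
| .5 | .870 | 13% |
| .7 | .717 | 28% |

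**5. Hypothesis 3 with one baseline mood covariate.** The SE ratio is √[(1 − r²)(1 + 1/106)], applied to the unadjusted interaction half-width of .376.

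| Assumed r with Stroop score | SE ratio | Interaction half-width |
|---|---|---|
| 0 | 1.005 | .378 |
| .1 | 1.000 | .376 |
| .2 | .984 | .370 |
| .3 | .958 | .360 |

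Break-even is r² = 1/107 = 0.9%. With a reliability of .49, no correlation with the interference score can be expected to exceed √.49 = .70, and realistic values are likely much lower.

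**6. Effect of a chance imbalance on the interaction.** A 1-SE imbalance in the baseline contrast shifts the estimate by r × 2/√28: .04, .08 and .11 SD at r = .1, .2 and .3.

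**The case against.** The strongest reply is that the Hypothesis 3 model is sound as written. Under randomisation its estimate is unbiased, and its interval already allows, on average, for chance imbalance in mood. The shifts in step 6 are part of the variance that the standard error counts. This stands: a reader might infer that leaving out baseline mood biases the interaction, and the documents do not support that.

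A reader might also take adjustment as a free gain in precision. For Hypothesis 3 that is not shown. The key correlation is unreported, the outcome is a difference score of modest reliability, and each covariate has a cost. With three covariates explaining nothing, the SE would be 1.4% larger. That is why one covariate is proposed and not several.

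The mood check may not need help. The partial test reported d of 1.24, 1.21 and .68 (Protocol, Preliminary Data), and at 56 per arm the unadjusted SE is √(2/56) = .19, so effects of that size would be plain anyway. This is fair. The gain there is in how precisely the induction effect is estimated, and its size rests on assumed correlations.

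Two further inferences go too far. Adjustment does not repair the removal, after randomisation, of participants who do not respond to the mood induction; baseline differences in the remaining set may be systematic. Nor do the documents make a case that sex must enter the model or that Hypothesis 4 needs the same covariate. Sex-specific dosing does not confound a randomised comparison. In Hypothesis 4 expectancies are not randomised, so adding mood would change what their coefficient means. Both are optional.

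Finally, the SAP does not say whether the balance check comes before or after exclusions, or whether R² is by cell or by factor. Step 3 shows that the conclusion does not depend on either reading.

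**Conclusion.** The point holds as an improvement, not as an error in the plan. The statement about the R² check is firm: on any reading of it, chance alone allows baseline differences of about a third to a half of an SD. A 0.4 SD difference looks small on the R² scale, and nothing is planned to follow.

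The case for adjusting the mood check is good, with an SE reduction of about 4% to 28% over assumed pre-post correlations of .3 to .7. The pre-score is taken before the drink, so the lower part of that range cannot be ruled out. The case for adjusting Hypothesis 3 is modest: between a 0.5% larger and a 4% smaller SE for r from 0 to .3. Its main merit is that the decision is made in advance. All figures use 28 per cell; at the SAP's 30 per cell the conclusions are unchanged.

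**What to change.** 1. **SAP, Statistical Design, mood check.** Compare the mood conditions on each post-manipulation subscale, adjusted for the same subscale's pre-manipulation score.
2. **SAP, Specific Aim 3, Analysis.** Prespecify one baseline mood covariate, either a named subscale or a defined composite, in the Hypothesis 3 model whatever R² is observed. Report the unadjusted model alongside it. Choose the covariate without reference to the Stroop scores.
3. **SAP, Statistical Design, baseline comparison.** Replace the confirmation with a descriptive table of baseline means and SDs by cell, and say whether it covers all randomised participants or the analysed set.

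The cost is SAP wording and one degree of freedom per model. No new data are needed. The downside is an SE about 0.5% larger if the covariate proves unrelated to the outcome. An analysis of all randomised participants is a separate need that this change does not meet.
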